## Offer of kits for partners of HIV positive clients

Individuals who test positive during PDHTC will be offered a self-test kit for their regular partner/s. Participants will be encouraged to check with their partner if they may want a self-test kit, and to check if the partner is happy to have their contact details passed on to study/program staff. In addition to the kit and instructional materials (a whatsapp version of the video will be shared with the participant if he/she has whatsapp) that are given as per clients taking the kits themselves, an information sheet that is addressed to partners will be enclosed. Only individuals who meet the following criteria will be eligible for taking kits to their partner:

- Willing to offer an HIV self-test kit to partner
- Willing to provide a telephone number that *must* be verified through ringing at time of kit distribution
- Willing to receive telephone calls from New Start staff. These calls will be to check whether the participant has given the kit to his/her partner, whether the partner tested, and whether, when or where the partner linked to confirmatory testing (if result of self-test was positive) male circumcision (if male and self-test result was negative), or PrEP, if at risk of HIV acquisition.
- Willing to give the partner's contact details for contact by the study team.

Clients will be told that a positive self-test result necessitates a confirmatory test, which must be provider-delivered. They will be told about possible places where confirmatory testing can be accessed if needed.

At two weeks after collection of kit, the client will be telephoned to ask if he/she gave the kit to the partner, whether the partner accepted it, whether the partner self-tested, and the result of the self-test if known. If the self-test was positive, they will be asked whether, when and where the partner sought confirmatory testing. Participants whose male partner's self-test result was negative will be asked whether, when and where the partners went for VMMC. Participants reporting that their partner obtained a negative self-test result will be asked if the partner linked to PrEP. This information will be updated on the participant's electronic record.

Participants who, at two weeks, had not yet given the kit to their partner (and report intention to do so), or those whose partner accepted the kit but had not tested at two weeks, or had not linked to services as applicable, will be given another call at 4 weeks and at three months. To ensure that participants' confidentiality is maintained and that telephone interviews are conducted with the correct person, staff who do the telephone calls will verify the following information before proceeding:

- Name of participant
- Date of birth
- Correct response to a 'password' question that is completed at time of kit collection according to participant's preference, for example name of primary school that was attended, mother's maiden family name, etc.

If the participant reports that the kit was given to her partner, at four weeks the partner will be telephoned to determine whether he/she self-tested, and the result of the self-test. If the self-test was positive, they will be asked whether, when and where they sought confirmatory testing. If the self-test result was negative and the partner is male, he will be asked whether, when and where he went for VMMC. Partners reporting a negative self-test result will be asked if, when where they linked to PrEP.

To ensure that the partner's confidentiality is maintained and that telephone interviews are conducted with the correct person, at time of collecting the kit from program staff, participants will be asked to share their 'password' information above with their partners. This information will be verified with the partner before the telephone interview can proceed.

## Offer of self-testing during PSI New Start mobile outreach

The New Start Centres also provide testing outreach. In Bulawayo and Harare, during outreach in urban areas, clients will be given information about HIVST and offered a choice between HIVST and PDHTC. Those who opt for self-testing will be given the test package, shown the instructional video, and given access to confidential on-site self-testing in a tent. At outreach facilities no option will be given for taking kits away for off-site testing. Clients will be asked to place their used test kits, together with the results form, in a dropbox that will be available at the outreach testing facility. Clients will be told that they do not need to share their self-test result with New Start staff. However it will be available at the outreach site on the same day. Such participants will be offered preferential access to PDHTC, as much as is feasible without breach of confidentiality of their HIVST result. To protect participant confidentiality and suspicion of HIV positive self-test from other people, outreach teams will also offer other services on site, including family planning, blood pressure and diabetes monitoring, VMMC and PrEP.

#### APPENDIX 1a: PRCEDURES FOR THE VISUAL STABILITY STUDY

#### Sample Collection at the New Start Centres Zimbabwe

Participants opting for testing onsite at New Africa House New Start Centre will be asked if they wish to enrol in the visual stability study (VSS). Participants will be talked through the information sheet and if they agree to participate will give verbal consent to participate.

The participant will enter one of eight booths at the New Start Centre in New Africa House to self-test in privacy. After the participant has performed and self-interpreted the OraQuick HIV self-test they will be asked to place the kit into an envelope along with their questionnaire which they will then place in the VSS study specific drop box as they exit the centre. The drop box will be emptied/ or switched every 10 minutes. The questionnaires will then be removed from the envelopes and filed. The test will then be given a new visual stability study (VSS) number, which will delink the test from the original participant who conducted the self-test. The test will then be re-read by the counsellor and research assistant independently following the instructions for use within 10 minutes of the box being emptied. This is to try and have the tests re-read within the test interpretation time window of 20-40 minutes. The re-read results should then be recorded on the daily record sheet next to its give VSS number. The test device should then be allowed to dry thoroughly before being stored at ambient temperature ready for transportation in envelops to the PSI laboratory. All kits should be stored out of direct sunlight and transported in robust boxes or envelopes.

All HIV self-test kits received at the PSI laboratory will be re-read independently on receipt by three different laboratory technicians blinded to the original results who have received training in the interpretation of HIV self-test devices. The HIV test device will then be incubated at ambient temperature in the laboratory. Humidity and temperature will be monitored daily and recorded using a min/max thermometer and hygrometer.

## **Data Collection**

All HIV self-test kits will be re-read (reactive, non-reactive, or invalid- no visual control line) by the three laboratory technicians one, two, three, four, five, six and seven days (excluding the weekend) after the first user reading. Additionally, the technicians will grade the intensity of the reactive test line (weak, moderate, strong). The grading will be done under strong artificial light. The technicians will also note and record confounding factors such as background colour, exogenous staining and any other damage.

Following the seven day re-reads, the HIV self-test kits will then be re-read by the three technicians at two, three and four weeks, and then at monthly intervals up to twelve months after the first user reading. The interpretations will be recorded on separate data sheets for each time point to ensure blinding of the data to previous results.

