## Analysis of Results

An interim analysis of the results will be reviewed at six months. All the recorded visual reads for each individual test result will be analysed for any change in the visualised test line. This will include a non-reactive test result changing to a reactive test result, an initial reactive test result changing to a non-reactive test result, an initial invalid test result changing to valid test result, an initial valid test result changing to an invalid test result. The intensities of the recorded lines will also be analysed for any

changes- strong to weak, weak to strong, weak to non-reactive etc. Any changes in the test devices will then be analysed against the daily recorded temperatures and humidity to look for any correlations.

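### Visual stability study: separate data sheets do not ensure blinding when the same three technicians re-read each kit about 20 times, so changes may be under-recorded

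*Protocol*

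**What the plan says.** Protocol Appendix 1a, under Sample Collection, assigns the identifier once, at the New Start Centre: "The test will then be given a new visual stability study (VSS) number, which will delink the test from the original participant". On arrival at the laboratory the kits are "re-read independently on receipt by three different laboratory technicians blinded to the original results".

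Under Data Collection, the later reads are made "by the three laboratory technicians one, two, three, four, five, six and seven days (excluding the weekend) after the first user reading", and the kits are then "re-read by the three technicians at two, three and four weeks, and then at monthly intervals up to twelve months". The technicians also grade the strength of a reactive line and note discolouration, staining and damage. The only protection described between one time point and the next is this: "The interpretations will be recorded on separate data sheets for each time point to ensure blinding of the data to previous results".

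Under Analysis of Results, the outcome is change within a kit: "All the recorded visual reads for each individual test result will be analysed for any change in the visualised test line". That section also covers shifts in line intensity, including a weak line becoming non-reactive.

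Section 4.3 gives the sample size: 307 kits for a precision of ±0.5% at an expected one-year change of 0.2%, raised to at least 340 for 10% loss.

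**The concern.** The outcome is whether a reading changes over time, so each read should be made without knowledge of the reads before it. The protocol accepts this, because it blinds the technicians to the original results and then says that separate sheets secure blinding between time points. A separate sheet stops a technician from looking up an earlier call. It does not stop a technician from recognising a kit by its number, its stain, its damage or an unusual line, and repeating the remembered call.

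The exposure is greatest in the first week, when reads are a day apart. It is also greatest where the call is a matter of judgement: a faint line, or the choice between weak, moderate and strong. Repeating a remembered call in those cases would hide the kind of change the study is meant to find. Independence among the three readers does not remove the problem, because each can anchor on his or her own earlier reading.

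**Working it through.** **1. The plan's own sample size.** Inputs from section 4.3: p = 0.002, d = 0.005, 95% confidence.

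n = z² p(1 − p) / d² = 1.96² × 0.002 × 0.998 / 0.005² = 306.7, so 307. This reproduces the stated figure. For 10% loss, 307 / 0.9 gives 342 and 307 × 1.1 gives 338; the stated 340 lies between them and leaves 306 after a 10% loss. The sample size is not in dispute.

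**2. Reads per technician per kit**, counted from Appendix 1a.

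- Days 1 to 7: seven are listed, five once the weekend is removed.
- Weeks 2, 3 and 4: three.
- Monthly to month 12: 11 if the four-week read stands for month 1, otherwise 12.
- Receipt in the laboratory: one, if counted.

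Lowest count: 5 + 3 + 11 = 19. With the receipt read: 20. Highest count: 7 + 3 + 12 + 1 = 23. So each technician sees each kit about 20 times.

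**3. Safeguards between reads.** Set side by side, the Sample Collection and Data Collection parts of Appendix 1a give:

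- same readers at every time point: yes;
- identifier changed between reads: not described;
- identifier masked at the read: not described;
- order of kits shuffled: not described;
- separate sheet per time point: yes.

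That the technician sees the number at each read is inferred from the single assignment and the absence of any masking step. The text does not say so outright.

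**4. Margin for missed changes.** Expected changed kits at the protocol's rate: 340 × 0.002 = 0.68 (307 kits: 0.61). Chance of no changed kit, even with perfect reading: 0.998^340 = 0.51.

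The documents give no rate of recall, so the share s of true changes that readers record is an assumption, shown over a range. The chance that at least one change is recorded among 340 kits is 1 − (1 − 0.002 s)^340:

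| Assumed share recorded, s | Chance of recording at least one change |
|---|---|
| 1.00 | 49% |
| 0.75 | 40% |
| 0.50 | 29% |
| 0.25 | 16% |

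The table shows how little room there is. It does not estimate the bias.

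**The case against.** Several counter-arguments have force.

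- **Recall is conjecture.** The documents contain no evidence of it. Remembering individual kits among about 340, many of them probably plain and non-reactive, across monthly gaps is uncertain. This stands, and it is why the point is a risk and not a demonstrated loss.
- **Direction.** A reader might infer that the error can only run towards apparent stability. The documents do not support that. A sheet for each time point suggests that readers know the kit's age, and expecting deterioration could push them towards recording change.
- **Size.** One could assume that a reader repeats a remembered call with probability a = 0.5 and require two of three readers to see the change at one session, and conclude that half of all changes are lost: (1 − a)³ + 3a(1 − a)² = 0.50. Analysis of Results contains no such rule; it examines all recorded reads for any change. Under the same assumption, with independent readers, at least one of three records the change with probability 1 − 0.5³ = 87.5% at one session and 1 − 0.5⁶ = 98.4% over two. Carry-over correlated between sessions would lower these figures, but nothing in the documents says by how much.
- **Small numbers.** Finding no change is about as likely as not even with perfect reading, and one kit in 340 is 0.29 percentage points, inside the planned ±0.5%. That fragility comes from the rare outcome and not from the blinding.
- **Existing safeguards.** The readers are trained, and blind to the original result on receipt, so their memory cannot hide a change between the counsellor's and research assistant's read and arrival at the laboratory. The criticised sentence also speaks of blinding the data, which separate sheets do achieve for the written record.
- **Level of detail.** Section 4.6 refers to standard operating procedures, and reading order could be left to one. But Appendix 1a sets out the procedures for this study and names the device it relies on, so it is fair to judge that device.

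What survives is that the stated device does less than the sentence claims, and that a cheap, better one exists.

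**Conclusion.** The point holds as a limited one. Three fixed technicians, about 20 reads per kit, an identifier assigned once and separate sheets as the only safeguard do not ensure blinding to earlier results. Changes may be under-recorded, especially in faint lines and intensity grades, and the first-week reads are the most exposed. The size is unknown and the net direction is not proven. With about 0.7 changed kits expected among 340, there is little margin, and the data could not separate a kit that did not change from one whose change went unrecorded.

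This rests on two assumptions: that technicians can see the number or recognise the kit, and that no unwritten shuffling takes place.

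A reader might go further and infer that reliance on late reads elsewhere in the programme is undermined. The protocol does use late reads, for example in section 4.2.3 to estimate HIV prevalence among self-testers, but it does not say that this substudy's result will be used to justify them. The cluster trial's primary outcome is not affected. This is a low-priority improvement.

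**What to change.** In Appendix 1a, Data Collection, replace the claim that separate sheets ensure blinding with a procedure:

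- at each session, present the kits in a fresh random order with the study number covered;
- record the read first, and only then reveal or scan the number to match it to the kit;
- keep a separate sheet per time point, and keep all three technicians reading every kit.

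Technicians should not be rotated. All three read every kit on each weekday of the first week, so keeping three reads without consecutive-day repeats would need at least six technicians. Changing readers would also mix disagreement between readers into the within-kit change that is analysed.

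The cost is a little handling time per session and a small risk of filing a read against the wrong kit, which scanning after the read limits. No extra kits or readers are needed and the sample size does not change. The procedure reduces recognition but does not abolish it: a distinctive stain remains visible, and the sheet still shows the kit's age. The revised text should therefore describe the steps and not promise complete blinding.

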## Analysis of Results

An interim analysis of the results will be reviewed at six months. All the recorded visual reads for each individual test result will be analysed for any change in the visualised test line. This will include a non-reactive test result changing to a reactive test result, an initial reactive test result changing to a non-reactive test result, an initial invalid test result changing to valid test result, an initial valid test result changing to an invalid test result. The intensities of the recorded lines will also be analysed for any

changes- strong to weak, weak to strong, weak to non-reactive etc. Any changes in the test devices will then be analysed against the daily recorded temperatures and humidity to look for any correlations.

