## 4.3 Pilot HIVST kit distribution at New Start HIV testing Centres

Distribution will occur in six geographic areas where New Start HIV testing services are offered in the following cities: Harare, Bulawayo, Chitungwiza, Masvingo, Mutare and Gweru. Three channels of

HIVST distribution will be employed: 1) distribution at static sites through the offer of a choice between PDHTC or HIVST; 2) distribution to partners of individuals who test HIV positive at the static sites, and 3) distribution during testing and counselling outreach in urban areas in Bulawayo and Harare. In this model we aim to:

- 1. Determine the acceptability of HIVST among individuals who seek HTS within New Start static and mobile sites in urban areas
- 2. Determine HIV yield among clients who are given HIV self-test kits compared to those who opt to test using PDHTC
- 3. Measure uptake of self-test kits for partners among clients who have tested HIV positive at New Start Static sites
- 4. Determine rates of linkage to HIV care, voluntary medical male circumcision (VMMC), and PrEP (offered to women aged 18-24) among individuals who are given HIV-self-test kits
- 5. Determine the cost and cost-effectiveness of providing HIVST through New Start HIV testing services

Detailed procedures are given in Appendix 1, Standard Operating Procedures (SOP) for the New Start Model.

Late read of returned used self-test kits will be done as detailed in the SOP. In addition, a visual stability study of used test kits will be done at New Africa House New Start Centre. Participants who give verbal consent for their used test kits to be anonymously used in the study will place their used test kit in a separate drop box that is earmarked for this purpose. This drop box will be emptied every ten minutes for immediate late read of results (as opposed to the regular drop box which will be emptied on a weekly basis. The visual stability study procedures are detailed in Appendix 1a. In brief, all test kits collected for the visual stability study will be re-read at regular intervals, under ambient conditions in the PSI laboratory, for a period of 12 months.

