340 participants will be recruited for the visual stability study. This sample size is justified as follows: based on a previous study by Choko *et al.* [27] the rate of change over a one year period for HIVST (Ora Quick) was 0.2%. Assuming there will be no difference in the proportion changing result, a sample size of 307 kits will provide precision of +/- 0.5% at the 95% confidence interval level. Therefore, we will collect at least 340 kits (this factors in a 10% loss).

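### Correlating kit changes with daily laboratory temperature and humidity can pick up kit age instead, and result changes are too few to correlate at all

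*Protocol*

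**What the plan says.** The visual stability study is described in protocol section 4.3 and Appendix 1a. At least 340 used kits from one New Start Centre are kept and re-read "under ambient conditions in the PSI laboratory, for a period of 12 months". Under Sample Collection, Appendix 1a says "The HIV test device will then be incubated at ambient temperature in the laboratory", and for the exposure record "Humidity and temperature will be monitored daily and recorded using a min/max thermometer and hygrometer". No second storage condition and no exposure record for individual kits is described.

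Under Data Collection, kits are re-read daily in the first week (weekends excluded), then "at two, three and four weeks, and then at monthly intervals up to twelve months after the first user reading". The clock for each kit is therefore its own age.

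Under Analysis of Results, the changes of interest are changes of result (reactive, non-reactive, invalid) and changes of line intensity. The closing sentence is "Any changes in the test devices will then be analysed against the daily recorded temperatures and humidity to look for any correlations". Kit age and collection date are not mentioned there.

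The sample size in section 4.3 rests on an earlier study in which "the rate of change over a one year period for HIVST (Ora Quick) was 0.2" (per cent), and states that "a sample size of 307 kits will provide precision of +/- 0.5% at the 95% confidence interval level". The length of the collection period is not given.

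**The concern.** On any given date every kit has the same recorded temperature and humidity, so the only contrast in exposure is calendar time. Kits collected close together pass through the seasons in the same order at nearly the same age. If lines fade or darken with age, change will line up with whatever the weather was doing at that age, even when temperature and humidity have no effect. Kits started as the weather cools would show one sign, and kits started as it warms would show the other.

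At stake is an exploratory statement about whether heat or humidity affects used kits. This has some practical weight: section 4.2.3 uses late reads of returned kits to estimate HIV prevalence among self-testers, and section 4.3 says that the regular drop boxes are emptied weekly. A false environmental signal could colour advice on storing and late-reading kits.

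A second problem is that the sentence covers changes of result as well as changes of intensity. At the protocol's own rate there is almost nothing of the first kind to correlate.

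**Working it through.** **1. The plan's own figure.** Inputs from section 4.3: p = 0.002, half-width d = 0.005, 95% confidence. n = 1.96² × p(1 − p) / d² = 306.7, so 307. This reproduces. For 10% loss, 307 / 0.9 = 341 and 307 × 1.1 = 338, so 340 is consistent.

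**2. Expected changes of result in 340 kits at 0.2%.**
- Expected number: 340 × 0.002 = 0.68 (307 × 0.002 = 0.61 with complete follow-up in 307).
- No change at all: 0.998³⁴⁰ = 0.506.
- Exactly one: 340 × 0.002 × 0.998³³⁹ = 0.345.
- At most one: 0.506 + 0.345 = 0.851, so two or more has probability 0.149.
- Five or more: 0.0007.

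With none or one event in 85% of studies, a correlation of result changes with temperature or humidity carries no usable information. Only line-intensity changes could supply enough data, and the protocol gives no rate for them.

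**3. Can ageing alone produce a correlation with temperature?** This was checked by simulation, one run per scenario. None of the following assumptions is in the protocol:
- 340 kits collected evenly over a window of varying length.
- Readings at days 1–5, 7, 14, 21 and 28, then every 30 days to day 360.
- Temperature following a yearly sine wave. The correlation does not depend on the size of the swing.
- A line score drifting linearly with age, plus noise with a standard deviation of about one fifth of the year's drift.
- No effect of temperature.

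Crude correlation of line score with temperature, by season in which collection starts:

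| Collection window | Warmest | Cooling | Coolest | Warming | Share of temperature variance explained by kit age |
|---|---|---|---|---|---|
| 1 day | −0.36 | +0.51 | +0.37 | −0.51 | about 100% |
| 30 days | −0.26 | +0.58 | +0.26 | −0.57 | 96–98% |
| 90 days | +0.01 | +0.52 | −0.01 | −0.51 | 76–82% |
| 180 days | +0.23 | +0.27 | −0.21 | −0.28 | 23–53% |
| 365 days | +0.04 | −0.01 | +0.02 | +0.06 | under 1% |

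After adjustment for kit age the correlation lies between −0.02 and +0.02 in every cell.

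**4. What adjustment costs in precision.** The variance of a temperature estimate is multiplied by 1 / (1 − R²), where R² is the share in the last column.
- 30 days: 1 / (1 − 0.959) = 24 to 1 / (1 − 0.984) = 63.
- 90 days: 1 / (1 − 0.759) = 4.1 to 1 / (1 − 0.823) = 5.6.
- 180 days: 1 / (1 − 0.231) = 1.3 to 1 / (1 − 0.529) = 2.1.

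With short collection, age adjustment removes the bias but leaves little information on temperature.

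**5. Limit of the check.** It uses a continuous score on all kits. The plan grades only reactive lines, as weak, moderate or strong, so fewer kits would contribute and chance variation would be larger. The mechanism is the same.

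**The case against.** The strongest reply is that the protocol names no model, test or significance level. It promises only to look for correlations, and the choice of covariates may sit in an analysis plan that is not shown. Kit age is known at every reading, so nothing prevents adjustment. This stands in part: the text does not rule out an age-adjusted analysis. But Appendix 1a does state the analysis, and as worded it sets changes against weather alone.

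A reader might infer that the correlation will necessarily reflect the season of collection. The documents do not support that. It needs a collection period well short of a year, and none is stated. Even with 90-day collection, two of the four start seasons give a correlation of about zero. A reader might take the 18-month chart in the study timelines to leave about three months for collection: approval runs to March 2016 and the chart ends in June 2017, which is 15 months, less 12 of follow-up. The chart does not list this sub-study, so it cannot settle the matter.

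Progressive change with age is also a premise rather than a statement of the protocol. It is what the repeated readings are designed to detect, but its size for line intensity is unknown. If lines do not change, there is nothing to confound.

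Nor should one infer that the stability result itself is undermined. The sample size targets the proportion of kits that change, and that estimate is unaffected. The few result changes make their correlation uninformative, not false.

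**Conclusion.** The concern holds in conditional form and is minor. With one shared exposure series and readings tied to kit age, a correlation that omits age can be spurious in either direction if lines change with age and collection is well short of a year. In the illustration the artefact is up to about ±0.58 for 30-day collection, up to ±0.28 for 180 days, and close to zero for a full year. These sizes rest on the assumed seasonal curve and linear drift, and show only what is possible.

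The point about result changes needs only the protocol's own 0.2% and 340 kits: 0.68 expected changes and a 51% chance of none. A correlation for result changes cannot usefully be estimated whatever the collection period.

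**What to change.** Replace the closing sentence of Analysis of Results in Appendix 1a with wording to this effect:

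- For line-intensity changes, analyse each reading. Include kit age at that reading, use the temperature and humidity recorded since that kit's previous reading, and allow for repeated readings of the same kit. Label the analysis exploratory. State the collection period, and say that the environmental estimate is imprecise if that period is short.
- List changes of result individually, with kit age and the recorded conditions, and do no test.
- Report the observed range of temperature and humidity as the conditions under which the stability result applies.

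The cost is a change of wording. Re-read results are already logged by kit number and time point, and temperature and humidity are recorded daily, so no new data are needed. The one drawback is that, with short collection, the age-adjusted analysis may say little about temperature or humidity. That would be an honest account of what the design can show.
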